3.2 Test of Cure Visit (Visit 2) Evaluations

The procedures listed below will be performed 7-14 days after randomization for the purpose of determining subject compliance/evaluability with drug administration and study instructions, evaluating the subject's response to therapy and whether or not additional treatment is needed (i.e. cure or failure), and obtaining information on concomitant medication use and possible adverse events.

- Review of Diary
- Assessment of Compliance: Subjects are queried to determine compliance with study drug administration and study instructions.
- Time to Symptom Resolution/Reoccurrence: Symptom resolution and reoccurrence will be assessed by review of the subject's diary and subject interview. Dates of symptom resolution and/or symptom recurrence should be documented.
- Subject Assessment of Symptoms: Subjects will be asked to rate their current vulvovaginal symptoms of itching, burning, and irritation as absent=0, mild=1, moderate=2, or severe=3. The sum of this symptom score will be added to the vulvovaginal signs score obtained during the pelvic examination to determine a combined symptom and sign severity score.
- Laboratory Tests and Specimen Collections: The lab tests listed below will be obtained at Visit 2.

- CBC with differential and blood chemistries (i.e. BUN, Creatinine, ALT, AST, ALP, and bilirubin) only for subjects enrolled in the Mixed Infection Study
- Vaginal culture for Candida species
- Vaginal Gram stain
- Pelvic Examination and Specimen Collections
 - Vulvovaginal signs rating
 - Vaginal discharge characterization
 - Vaginal pH measurement
 - KOH Whiff Test
 - Saline wet mount
 - Vaginal Candida culture
 - Vaginal Gram stain
- Assessment of Clinical Status, Need for Additional Treatment: Following subject evaluation, the investigator/clinician will be asked to document whether the subject requires any additional treatment for vaginal discomfort/symptoms. Subjects who do require additional treatment should be treated per investigator/clinician judgment and terminated from the study. Subjects who do not require treatment (and subjects who did not self-medicate) may remain in the study and return for their regularly scheduled follow up visit (Visit 3).
- Determination of Cure or Failure of Subject's Enrolled Infection:
 - BV subjects must satisfy all three of the clinical criteria listed below in order to be considered a BV cure (i.e. clinical cure).
 - Discharge has returned to normal/physiologic¹

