 - The whiff test is negative for any amine "fishy" odor.
 - The saline wet mount is < 20% clue cells.

If in the investigator/clinician's opinion the subject requires additional treatment for BV or if the subject self-administered drug therapy for vaginal discomfort/symptoms after completing therapy, the subject will be considered a BV failure².

 - VVC subjects must have all signs and symptoms attributable to VVC resolved (i.e. clinical cure), in order to be considered a VVC cure. If in the investigator/clinician's opinion the subject requires additional treatment for VVC or if the subject self-administered drug therapy for vaginal discomfort/symptoms after completing therapy, the subject will be considered a VVC failure².
 - A Mixed Infection cure is a subject who meets the definition of a BV cure AND a VVC cure. If in the investigator/clinician's opinion the subject requires additional treatment for either BV, VVC, or Mixed Infection or if the subject self-administered drug therapy for vaginal discomfort/symptoms after completing therapy, the subject will be considered a Mixed Infection failure.

1. In the event a subject treated for BV gets a secondary yeast infection following treatment and discharge is consistent with VVC (i.e. white, creamy, and curdy [cottage cheese like] adherent to the epithelium), the subject will be considered a clinical cure providing all other clinical criteria for BV cure are met and the subject has a positive yeast culture.

2. Self-administration of therapy includes prescription and OTC antimicrobial, anti-fungal, analgesics, or steroid treatments.

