4.3 Efficacy Endpoints and Evaluations

The primary and secondary endpoints are reflective of each of the infection studies within the protocol. These include:

Primary Endpoints

- BV Study: BV cure rate, with cure defined as normal/physiologic discharge, negative whiff test, and < 20% clue cells (i.e. clinical cure)
- VVC Study: VVC cure rate, with cure defined as resolution of all signs and symptoms attributable to VVC (i.e. clinical cure)
- Mixed Infection Study: Mixed Infection cure rate, with cure defined as BV cure (i.e. BV clinical cure) AND a VVC cure (i.e. VVC clinical cure)

Primary efficacy endpoint evaluations will occur at the test-of-cure Visit 2.

If a subject requires additional treatment for vaginal discomfort/symptoms (i.e. a BV subject requiring treatment for BV, a VVC subject requiring treatment for VVC or a Mixed Infection subject requiring treatment for BV and/or VVC) prior to or at Visit 2, the subject will be considered a treatment failure. These subjects will be evaluable for the modified intent-to-treat (mITT) and the per-protocol (PP) population analyses, providing all other evaluability criteria for these population groups have been met.

Additionally, if a subject self-medicates herself for vaginal discomfort/symptoms at any time prior to Visit 2, the subject will be considered a treatment failure. If this occurs, the subject will remain evaluable for the mITT analyses but will be non-evaluable for the PP analysis.

Secondary Endpoints

Note, for BV a Gram stain Nugent score cure will be defined as a score of < 4, i.e. 0 – 3.

- BV Study: BV clinical and Gram stain Nugent score combined cure rate, and Gram stain Nugent score cure rate alone; changes/improvements in Amsel criteria and Nugent scores; time to resolution of symptoms
 - In addition, cure rates over time will be explored
- VVC Study: VVC clinical and mycologic cure rates combined and mycologic cure alone; changes/improvements in signs and symptoms scores; eradication (or persistence) of individual fungal species; time to resolution of symptoms
- Mixed Infection Study: BV clinical and Gram stain Nugent score cure rates alone and combined; changes/improvements in Amsel criteria and Nugent scores; VVC clinical and mycologic cure rates alone and combined; changes/improvements in signs and symptoms scores; eradication or persistence of individual fungal species; time to resolution of symptoms

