4.5 Determination of Sample Size

Approved labeling, clinical data included in New Drug Applications and approval packages, and sponsor experience with the compounds in this study and similar therapies provide the following estimates and ranges of the cure rates (as proportions) for the treatments within each infection study.

1. BV Subjects
 - a. BV Gel (0.9% metronidazole gel): .50 (.45-.55)
 - b. Placebo Gel: .20 (.15-.25)
2. VVC Subjects
 - a. VVC Gel (0.8% terconazole gel): .70 (.65-.75)
 - b. Placebo Gel: .20 (.15-.25)
3. Mixed Infection Subjects
 - a. Combo Gel (0.9% metronidazole gel and 0.8% terconazole gel): .35 (.30-.40)
 - b. VVC Gel (0.8% terconazole gel): .10 (.05-.15)
 - c. BV Gel (0.9% metronidazole gel): .10 (.05-.15)

Under the assumption that the above estimated cure rates are true for the population, sample sizes were calculated for each infection study based on these estimates for at least 90% power and at least 50 subjects per treatment group. Superiority tests will be performed as two-sided, $\alpha = 0.05$ level significance tests, and sample sizes were calculated using Fisher's Exact test in case the planned Chi-squared test is not appropriate.

The following table provides the sample size required for each treatment group within each infection study. The total sample size is given, and represents the number of evaluable subjects required (Per Protocol population). Entry in each infection study of the trial will be stopped when this number of evaluable subjects is reached, since evaluable/not-evaluable can be determined from the completed case report form prior to unblinding.

Required Number of Evaluable Patients, by Infection Study and Treatment Group							
Study:	BV Only Patients		VVC Only Patients		Mixed Infection Only Subjects		
Treatment Arm:	BV Gel	Placebo Gel	VVC Gel	Placebo Gel	BV Gel	VVC Gel	Combo Gel
Expected Cure Rate	50%	20%	70%	20%	10%	10%	35%
n for at least 80% Power, and at least 50 per group	58	58	50	50	63	63	63
Actual Power	90.0%		> 99.9%		90%		
Total N	405						

Thus, subjects will be enrolled until approximately 405 evaluable subjects, as indicated above, for all three infection studies, have completed the trial.

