4.7.2 Secondary Efficacy Analyses

Secondary efficacy endpoints are listed in [Section 4.3](#). These endpoints include variables that are categorical (including binary variables), ordinal (such as rating scores), or time to event variables (such as time to resolution of symptoms). The analysis of the secondary endpoints will be performed using the mITT population with worst case scenario imputation for missing data, with supportive analyses conducted using the PP population.

For the secondary endpoints that are categorical or ordinal with four or fewer levels (including binary outcome variables), the analysis will include the proportion of subjects with each criteria or each score, at baseline and endstudy. The comparison of treatment groups will be performed using Chi-squared tests if all expected cell counts are at least 5, and Fisher's Exact test otherwise. For binary outcomes, (clinical outcome, mycological outcome, and eradication [or persistence] of individual fungal species) 95% two-sided confidence intervals for the difference in proportions will also be constructed using the continuity corrected Wald intervals when Chi-square tests are appropriate, or the method of Chan and Zhang (1999) otherwise.

Secondary endpoints that are ordinal data with more than four levels, such as Nugent score, the median score at baseline, endstudy, and the change from baseline will be computed, in addition to the proportion of subjects at each level. Treatment comparisons will be performed using the Wilcoxon Rank Sum test.

The secondary endpoint of time to resolution of symptoms will be analyzed in each infection study by arm using log-rank tests to compare arms within each study and Kaplan-Meier plots. Kaplan-Meier estimates of the quartiles for time to resolution will be computed, along with 95% confidence intervals. Censoring times for the Kaplan-Meier estimates will be based on the date of last contact or visit 3 (whichever is earliest) if symptoms never resolved or the patient was an early withdrawal and status is unknown.

The analysis of eradication (persistence) of individual fungal species will be conducted in subgroups of subjects defined by fungal species present at baseline (for the VVC and Mixed Infection studies).

In addition, for each study a summary will be made of subjects classified as:

- Persistent Infection – no cure at Visit 2 or Visit 3
- Persistent Cure – cure at Visit 2 and Visit 3
- Late Cure – no cure at Visit 2 but cure at Visit 3

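### Under section 4.7.2, symptom resolution recorded after self-medication before Visit 2 counts as an event in the time-to-resolution analysis, although section 4.3 scores the same subject a treatment failure; this may dilute the treatment difference by an amount the SAP does not allow one to compute

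*SAP*

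**What the plan says.** - **Analysis.** SAP 4.7.2: "The secondary endpoint of time to resolution of symptoms will be analyzed in each infection study by arm using log-rank tests", with Kaplan-Meier plots and quartiles. Secondary endpoints are analysed in mITT with worst-case imputation of missing data, and with supportive PP analyses.
- **Censoring.** The same section censors at last contact or Visit 3, whichever is earlier, in two cases: symptoms never resolved, or the subject withdrew early and her status is unknown.
- **Source of the dates.** SAP 3.2 takes them from the diary and the interview: "Dates of symptom resolution and/or symptom recurrence should be documented". It does not require that no other drug was used.
- **Primary endpoint.** SAP 4.3: "if a subject self-medicates herself for vaginal discomfort/symptoms at any time prior to Visit 2, the subject will be considered a treatment failure". Such a subject stays in mITT and leaves PP. A subject who needs additional treatment for the enrolled infection at or before Visit 2 is also a failure, but can stay in PP.
- **What self-medication covers.** A footnote in SAP 3.2: "Self-administration of therapy includes prescription and OTC antimicrobial, anti-fungal, analgesics, or steroid treatments".
- **Early termination.** SAP 1.2 terminates subjects who self-medicated, so they do not go on to Visit 3.
- **Outputs.** Table 14.2.19 (time to resolution) is listed for mITT only, and Figure 14.2.20 names no population.

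**The concern.** The drugs in the footnote can themselves relieve itching, burning and irritation. A subject who takes one because her symptoms persist, and who then improves, has a recorded resolution date. The censoring rule does not remove that date, so relief from another drug is credited to her randomised arm. The subject who is a failure in the primary table can be a resolution in Table 14.2.19.

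The subjects most likely to reach for another drug are those whose symptoms have not gone. If control arms hold more of them, as one would expect if the treatments work, the control curve is raised more than the active curve. The log-rank comparison then moves towards no difference and the reported control quartiles shorten. At stake is the interpretation of one secondary endpoint in each of the three studies.

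**Working it through.** **Step 1. Trace one subject through the rules.** Suppose she self-medicates on day 5, her symptoms stop on day 7, and the diary is reviewed at Visit 2.

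| Rule | Result |
|---|---|
| 4.3, primary endpoint | Treatment failure, in mITT |
| 4.7.2, never resolved | Does not apply: a resolution is recorded |
| 4.7.2, early withdrawal with status unknown | Does not apply: status is known |
| 4.6 and 4.7.2, worst-case imputation | Does not apply: the date is not missing |
| Time to resolution, mITT | Event on day 7 |

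Termination under 1.2 does not undo this, because Visit 2 includes the diary review.

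**Step 2. The plan's own figures.** SAP 4.5 sizes the studies "based on these estimates for at least 90% power and at least 50 subjects per treatment group", with Fisher's exact test at two-sided 0.05. Exact enumeration gives:

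| Study | n per group | Cure rates | Recomputed power | Stated |
|---|---|---|---|---|
| BV | 58 | 0.50 v 0.20 | 0.906 | 90.0% |
| VVC | 50 | 0.70 v 0.20 | 0.9994 | > 99.9% |
| Mixed, per comparison | 63 | 0.35 v 0.10 | 0.906 | 90% |

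The total is 2×58 + 2×50 + 3×63 = 405, as stated. These figures concern cure. The SAP states no event rate, hazard ratio or power for time to resolution, and no self-medication rate. Steps 3 to 5 therefore rest on assumptions.

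**Step 3. Direction, with equal rates in both arms.** Let p be the share that resolves on study drug, s the share of unresolved subjects who self-medicate before Visit 2, and 0.8 the assumed share of those who then report relief. The recorded share resolved is p + 0.8s(1 − p), so the between-arm difference becomes (p1 − p2)(1 − 0.8s). For s = 10%, 20% and 30% the factor is 0.92, 0.84 and 0.76. With cure rates standing in for resolution rates:

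- BV: 30 points becomes 27.6, 25.2, 22.8.
- VVC: 50 points becomes 46, 42, 38.
- Mixed: 25 points becomes 23, 21, 19.

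**Step 4. Illustration A: log-rank power, same s in both arms.** Resolution on study drug is uniform over days 2–10, and relief after self-medication falls on days 5–10. Where two values are given, they come from runs of 3000 and 2000 simulated trials.

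| Study | s = 10% | s = 20% | s = 30% | Self-medicators as not resolved |
|---|---|---|---|---|
| BV | 0.87 / 0.86 | 0.81 / 0.81 | 0.72 / 0.72 | about 0.92–0.94 |
| Mixed, one comparison | 0.85 / 0.82 | 0.74 / 0.71 | 0.63 / 0.62 | about 0.93–0.94 |
| VVC | 0.998 | 0.99 | 0.98 | about 1.00 |

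At s = 2%, power is about 91% (BV) and 92% (Mixed).

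**Step 5. Illustration B: another time model, unequal rates.** Exponential times are set so that the cure rate is the share resolved by day 10. Self-medication falls on days 4–8, 80% are relieved two days later, and 600 trials are run per row. Entries are hazard ratios for resolution.

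| Study, s active / s control | As written | Held unresolved to day 30 | Censored at self-medication |
|---|---|---|---|
| BV 10/10 | 2.89 | 3.05 | 3.22 |
| BV 10/30 | 2.14 | 3.73 | 3.13 |
| VVC 10/10 | 5.45 | 5.47 | 6.18 |
| VVC 10/30 | 3.85 | 6.39 | 5.74 |
| Mixed 10/10 | 3.26 | 3.77 | 3.93 |
| Mixed 10/30 | 2.08 | 4.51 | 3.73 |
| BV 30/10 | 3.37 | 2.34 | 3.37 |

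Power as written at 10/30 is 0.90 (BV), 0.85 (Mixed) and 1.00 (VVC). With self-medicators held unresolved it is 1.00 in all three. The hazard ratios are one-step approximations. With no self-medication they average 3.26, 6.36 and 3.95, against input values ln(0.5)/ln(0.8) = 3.11, ln(0.3)/ln(0.8) = 5.40 and ln(0.65)/ln(0.9) = 4.09. Rows should be read across, not as absolute values.

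**The case against.** **No explicit event definition.** Section 4.7.2 never says in words that relief after self-medication counts. That is correct; the result follows from its censoring rules and the absence of any condition on the date. Nothing extends the failure rule of 4.3 to this endpoint.

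**PP drops these subjects.** This stands in part. Self-medication before Visit 2 makes a subject non-evaluable for PP, so the planned supportive analysis would exclude her. But no PP table is listed, and subjects who needed additional treatment can remain in PP under 4.3.

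**Cure rates are the wrong proxy.** This stands. BV cure is normal discharge, a negative whiff test and fewer than 20% clue cells; none is a subject-rated symptom. The minimum sign and symptom score in 3.1 applies to VVC and Mixed entry, not to BV. A BV failure may have no rated symptom and no reason to self-medicate. Mixed cure contains the same BV criteria. A reader might take the BV and Mixed power figures above as expected losses; the documents do not support that.

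**Dilution is not certain.** This also stands. A reader might infer that the treatment difference must shrink. If active subjects self-medicate more often (BV 30/10), the rule as written gives a larger hazard ratio than holding self-medicators unresolved.

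**Counting relief whatever else was taken is a legitimate choice.** It is, and it can differ from the primary result without contradiction because it measures something else. But the SAP does not declare that choice, and its own rule for the primary endpoint goes the other way.

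**Conclusion.** The point holds. Followed exactly, 4.7.2 counts a documented resolution after self-medication or additional therapy before Visit 2 as an mITT event, while 4.3 scores the same subject a failure. If unresolved control subjects take other drugs at least as often as unresolved active subjects, the treatment difference tends to be diluted.

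The size cannot be derived from the SAP. The illustrations range from negligible to large and depend on the assumed self-medication rates, the 80% relief rate, the time model, and cure rates standing in for symptom resolution. They also use the evaluable (PP) group sizes, whereas the analysis is in mITT. VVC power stays at 0.98 or more throughout.

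A reader might infer that the superiority claims are at risk. They are not: the primary endpoint is protected by 4.3, and this is a secondary endpoint. The change is nevertheless worth making before unblinding, because the rule is fixed in a way that conflicts with the SAP's own treatment of these subjects and is easily put right.

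**What to change.** Add to 4.7.2:

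1. A resolution date is an event only if it precedes any self-administered or additional therapy for vaginal discomfort or symptoms.
2. Subjects who take such therapy before resolution are analysed as not resolved and censored at the end of the Visit 3 window (day 30). Without this, the present rule would censor them at their early last contact, which is probably informative because they are terminated under 1.2.
3. Two sensitivity analyses are shown: all recorded dates as events, and censoring at the start of such therapy.

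Add a PP time-to-resolution table to the list of outputs and state the population of Figure 14.2.20. Confirm that start dates of such therapy are recorded with concomitant medications; the SAP lists these medications (Listing 16.1.16) but does not mention start dates.

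The cost is a few sentences, one programming condition and some extra output. The downside is that the endpoint becomes resolution without other treatment, so resolution rates will be slightly lower in every arm.

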1.2 Study Design

This is a multi-center, phase III trial, comprised of three studies, each designed to test the safety and efficacy of a different investigational product, for a specific vaginal infection/indication. They are:

1. Bacterial Vaginosis (BV) Study: A randomized, double-blind, parallel-group, placebo-controlled study to test the safety and efficacy of BV Gel (0.9% metronidazole gel) for the treatment of BV
2. Vulvovaginal Candidiasis (VVC) Study: A randomized, double-blind, parallel-group, placebo-controlled study to test the safety and efficacy of VVC Gel (0.8% terconazole gel) for the treatment of VVC
3. Mixed Infection (Concurrent BV and VVC) Study: A randomized, double-blind, parallel-group, active-controlled study to test the safety and efficacy of Combo Gel (0.9% metronidazole gel and 0.8% terconazole gel) for the treatment of Mixed Infection

All study medication is intravaginal and will be dosed as one applicator for three consecutive days. Subjects who sign an informed consent form (ICF), are diagnosed with BV, VVC, or Mixed Infection, and meet eligibility requirements will be enrolled into the appropriate infection study and subsequently

randomized to treatment based on clinical diagnosis at the screening and enrollment/baseline visit (Visit 1). BV subjects will be entered into the BV Study, VVC subjects will be entered into the VVC Study, and concurrent BV and VVC (Mixed Infection) subjects will be entered into the Mixed Infection Study.

All subjects will be asked to return for a test of cure visit (Visit 2) 7-14 days after randomization. If a subject is menstruating on the day of the scheduled visit, she should be rescheduled to return 24 hours after completion of menses. Subjects who in the opinion of the investigator/clinician require additional treatment for vaginal discomfort/symptoms and subjects who self-medicated for vaginal discomfort/symptoms, will be terminated from the study. All other subjects will return for a follow-up evaluation visit (Visit 3) 21-30 days after randomization.

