3.3 Follow Up Visit (Visit 3) Evaluations

The following procedures will be performed 21-30 days after randomization for the purpose of determining subject compliance; determining either presence or absence of the subject's baseline infection and whether or not additional treatment is needed; and obtaining information on concomitant medication use and possible adverse events.

If a subject was unable to return for Visit 2 but returns for Visit 3, available information that was to be obtained at Visit 2 regarding study drug administration/compliance and time to resolution/reoccurrence of symptoms may be obtained at Visit 3. The subject's diary should be reviewed and unused drug collected. Subjects in the Mixed Infection Study who missed Visit 2 should have hematology and chemistry labs obtained.

- Assessment of Compliance: Subjects are queried to determine compliance with study drug administration and study instructions.
- Subject Assessment of Symptoms: Subjects will be asked to rate their current vulvovaginal symptoms of itching, burning, and irritation as absent=0, mild=1, moderate=2, or severe=3. The sum of this symptom score will be added to the vulvovaginal signs score obtained during the pelvic examination to determine a combined symptom and sign severity score.
- Laboratory Tests and Specimen Collections: The lab tests listed below will be obtained at Visit 3.
 - Vaginal culture for Candida species
 - Vaginal Gram stain
- Pelvic Examination and Specimen Collections
 - Vulvovaginal signs rating
 - Vaginal discharge characterization
 - Vaginal pH measurement
 - KOH Whiff Test
 - Saline wet mount
 - Vaginal Candida culture
 - Vaginal Gram stain
- Assessment of Clinical Status, Need for Additional Treatment: Following subject evaluation, the investigator/clinician will be asked to document whether the subject requires any additional treatment for vaginal infection. Subjects who do require additional treatment should be treated per investigator/clinician judgment.
- Subject Satisfaction Survey: Subjects should be given the Subject Satisfaction Survey and asked to complete the form before leaving the clinic. Completion of the survey is voluntary and does not affect participation in the study in any way.

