14.2 Efficacy Summaries

Table 14.2.1.1	Summary of Primary Endpoint for BV Study – Test-of-Cure, mITT Population
Table 14.2.1.2	Summary of Primary Endpoint for BV Study – Test-of-Cure, PP Population
Table 14.2.2.1	Summary of Primary Endpoint for VVC Study – Test-of-Cure, mITT Population
Table 14.2.2.2	Summary of Primary Endpoint for VVC Study – Test-of-Cure, PP Population
Table 14.2.3.1	Summary of Primary Endpoint for Mixed Infection Study – Test-of-Cure, mITT Population
Table 14.2.3.2	Summary of Primary Endpoint for Mixed Infection Study – Test-of-Cure, PP Population
Table 14.2.4	Exploratory Analysis of Primary Endpoint by Month of Study, For Patients Receiving BV Gel – Test-of-Cure, mITT Population
Figure 14.2.5	Time Plot of Primary Endpoint by Month of Study, For Patients Receiving BV Gel – Test-of-Cure, mITT Population
Table 14.2.6	Summary of Visit 2 Symptom and Sign Severity Score, mITT Population
Table 14.2.7	Summary of Visit 2 Pelvic Exam, mITT Population
Table 14.2.8	Summary of Visit 2 Compliance Assessment, mITT Population
Table 14.2.9	Summary of Visit 2 Need for Additional Treatment, mITT Population
Table 14.2.10.1	Summary of Visit 2 BV Clinical Cure, mITT Population
Table 14.2.10.2	Summary of Visit 2 BV Clinical Cure, PP Population
Table 14.2.11.1	Summary of Visit 2 VVC Clinical Cure, mITT Population
Table 14.2.11.2	Summary of Visit 2 VVC Clinical Cure, PP Population
Table 14.2.12.1	Summary of Visit 2 Gram Stain Cure, mITT Population
Table 14.2.12.2	Summary of Visit 2 Gram Stain Cure, PP Population
Table 14.2.13.1	Summary of Visit 2 Candida Culture Cure, mITT Population
Table 14.2.13.2	Summary of Visit 2 Candida Culture Cure, PP Population
Table 14.2.14.1	Summary of Visit 2 Combined BV Clinical and Gram Stain Cure, mITT Population
Table 14.2.14.2	Summary of Visit 2 Combined BV Clinical and Gram Stain Cure, PP Population
Table 14.2.15.1	Summary of Visit 2 VVC Clinical and Candida Culture Cure, mITT Population
Table 14.2.15.2	Summary of Visit 2 VVC Clinical and Candida Culture Cure, PP Population

Table 14.2.16	Summary of Visit 2 Change in Pelvic Exam Results, mITT Population
Table 14.2.17	Summary of Visit 2 Change in Signs and Symptoms, mITT Population
Table 14.2.18	Summary of Visit 2 Eradication/Persistence of Candida Species, mITT Population
Table 14.2.19	Summary of Time to Resolution of Symptoms, mITT Population
Figure 14.2.20	Kaplan-Meier Curve of Time to Resolution of Symptoms

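### Time to symptom resolution: subjects who leave because symptoms persist are censored like withdrawals of unknown status, so Kaplan-Meier estimates can overstate resolution without further treatment

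*SAP*

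**What the plan says.** Section 4.7.2 analyses time to resolution of symptoms with log-rank tests, Kaplan-Meier plots, and quartiles with 95% confidence intervals. On censoring it says: "Censoring times for the Kaplan-Meier estimates will be based on the date of last contact or visit 3 (whichever is earliest) if symptoms never resolved". The same sentence applies the rule to early withdrawals whose status is unknown. Section 14.2 reports the endpoint in Table 14.2.19, "Summary of Time to Resolution of Symptoms, mITT Population", and Figure 14.2.20.

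Who leaves before Visit 3 is set elsewhere:
- Section 3.2, at Visit 2 (days 7-14): "Subjects who do require additional treatment should be treated per investigator/clinician judgment and terminated from the study".
- Section 1.2 adds that "subjects who self-medicated for vaginal discomfort/symptoms, will be terminated from the study".
- Everyone else goes on to Visit 3 (days 21-30).

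Section 4.3 classes as treatment failures those who need additional treatment for the enrolled infection before or at Visit 2, and those who self-medicate at any time before Visit 2.

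On dating of resolution, section 3.2 says for Visit 2: "Dates of symptom resolution and/or symptom recurrence should be documented". For subjects who missed Visit 2, section 3.3 says that information on "time to resolution/reoccurrence of symptoms may be obtained at Visit 3".

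Section 4.7.2 also carries a general sentence for secondary endpoints: "The analysis of the secondary endpoints will be performed using the mITT population with worst case scenario imputation for missing data".

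**The concern.** Kaplan-Meier assumes that a censored subject has the same later chance of resolving as those still under observation. Here the subjects censored around Visit 2 are largely those who left because symptoms persisted and treatment was judged necessary, or was taken. Those still observed were judged not to need it. The method gives the first group the later resolution rate of the second, which pushes the curve up.

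The same women are failures in the primary endpoint, so the two analyses treat one outcome differently. In an arm with little early resolution, a quartile could be reported that would not be reached if these women were kept as not resolved. The SAP also leaves open what counts as last contact, whether resolution dates after Visit 2 are used, and how resolution after additional treatment or self-medication is counted.

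**Working it through.** The SAP gives no figure for this endpoint, so there is none to reproduce. It fixes the visit windows and the censoring rule. The rates below are assumptions.

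**Step 1: two-period algebra.** Let r be the share resolved by Visit 2, f the share of the unresolved who are terminated at Visit 2, and g the share of the remaining unresolved who resolve between Visits 2 and 3.
- Planned rule (terminated subjects censored at Visit 2): 1 - (1 - r)(1 - g).
- Alternative (terminated subjects kept as not resolved): r + (1 - r)(1 - f)g.
- Difference: (1 - r) × f × g, which is positive whenever f and g are, and zero if either is zero.

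With f = 0.6 and g = 0.1:
- r = 0.2: 1 - 0.8 × 0.9 = 28.0% against 0.2 + 0.8 × 0.4 × 0.1 = 23.2%, a difference of 4.8 points.
- r = 0.5: 1 - 0.5 × 0.9 = 55.0% against 0.5 + 0.5 × 0.4 × 0.1 = 52.0%, 3.0 points.
- r = 0.7: 1 - 0.3 × 0.9 = 73.0% against 0.7 + 0.3 × 0.4 × 0.1 = 71.2%, 1.8 points.

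**Step 2: staggered visit dates.** This was simulated with 200,000-400,000 subjects per case. Visit 2 was uniform on days 7-14 and Visit 3 on days 21-30, with 60% of the unresolved terminated at Visit 2. Early resolution was spread either over days 1-7 or up to the subject's own Visit 2. Estimates at day 30:

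| Resolved by Visit 2 | Late resolution among the rest | Early timing | Planned | Kept as not resolved | Excess (points) |
|---|---|---|---|---|---|
| 20% | none | days 1-7 | 20.0% | 20.0% | 0.0 |
| 20% | none | to own Visit 2 | 21.7% | 20.0% | 1.7 |
| 20% | 10% | days 1-7 | 29.6% | 23.5% | 6.1 |
| 20% | 10% | to own Visit 2 | 30.9% | 23.3% | 7.6 |
| 50% | none | days 1-7 | 50.0% | 50.0% | 0.0 |
| 50% | none | to own Visit 2 | 53.8% | 50.0% | 3.8 |
| 50% | 10% | days 1-7 | 55.9% | 52.0% | 3.8 (before rounding) |
| 50% | 10% | to own Visit 2 | 59.3% | 52.1% | 7.2 |

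The rows with no late resolution show that late dates are not essential. A failure censored on day 7 is given the resolution rate of subjects still awaiting Visit 2 on days 8-14.

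**Step 3: quartiles.** With 20% resolved and 10% late, the first quartile is day 21 (days 1-7 timing) or day 18 (own-Visit-2 timing) under the plan, and not reached under the alternative. With 50% resolved and 10% late, the first quartile is unchanged, and the median moves clearly only with own-Visit-2 timing (day 12 against 14). With 60-70% resolved, neither changes.

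**Step 4: departures before Visit 2.** Section 4.3 foresees additional treatment or self-medication before Visit 2. If 30% of the terminated subjects leave on days 3-7, the planned curve is already about 1-2 points higher by day 7.

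**Step 5: meaning of last contact.** If last contact falls 7 days after Visit 2, the excess in the 10%-late cases drops to 4.1-4.2 points (20% resolved) and 2.6-2.7 points (50% resolved).

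**Step 6: comparison of arms.** Log-rank rejection rates, 58 per arm, 3,000 runs, 10% late, planned against alternative, for the two timings in turn:
- 50% against 20% resolved, 60% terminated in both arms: 0.918 against 0.916; 0.904 against 0.906.
- Identical arms: 0.053 against 0.052; 0.056 against 0.059.
- 50% against 20% resolved, termination 30% in one arm and 80% in the other: 0.922 against 0.955; 0.885 against 0.963.

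The bias in the day-30 difference between the 50% and 20% arms has no fixed sign. From the table, with 10% late it is 3.8 - 6.1 = -2.3 or 7.2 - 7.6 = -0.4 points. With none late and own-Visit-2 timing it is 3.8 - 1.7 = +2.1.

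**The case against.** **The dating procedures favour a small bias.** Section 3.2 plans dating at Visit 2. Section 3.3 provides for it at Visit 3 only for subjects who missed Visit 2. The class in section 4.7.2 defined as "no cure at Visit 2 but cure at Visit 3" is a cure status by visit, not a dated symptom event. If no later dates exist and early resolution falls in days 1-7, the excess is zero. This stands as a limit on the size. It does not remove the problem: censoring runs out to Visit 3, the SAP does not say that later dates are excluded, and staggered Visit 2 dates alone can produce an excess.

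**The target is not stated.** Censoring at additional treatment can serve a different question, namely resolution had no such treatment been given. That is fair, and the overstatement is claimed only for resolution without further treatment. But the SAP names no such question, and the hypothetical reading would still need the assumption that treated subjects resemble those who did not need treatment.

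**The worst-case sentence might seem to cover it.** That sentence concerns missing data. A known unresolved status is not missing, and the specific censoring sentence governs.

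**The illustrations sit near thresholds.** With 30% resolved by Visit 2, 60% terminated and 10% late, the first quartile is the same under both rules (day 6 or day 9, by timing). The median shift arises at exactly 50% resolved; at 55% it is day 10 against 11. Own-Visit-2 timing also ties resolution to the appointment date. All of this stands.

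A reader might also infer that the curve is safe through day 7. The documents do not support that, because section 4.3 allows treatment and self-medication before Visit 2.

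**Conclusion.** The point holds. Followed as written, section 4.7.2 censors known non-resolvers informatively and out of line with the primary endpoint. Kaplan-Meier estimates and quartiles can be too high if read as resolution without further treatment.

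The SAP does not determine the size. The excess is zero if all resolutions fall in days 1-7, no later dates are used and nobody is treated or self-medicates before Visit 2. It is about 2-8 points at day 30 in most illustrative cases with 20-70% resolved by Visit 2, 60% of the unresolved terminated and 0-10% of the rest resolving late. Small effects before day 7 are possible.

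A reader might infer that the treatment comparison is compromised, or tilted towards the active gel. The calculations do not support this. The log-rank test hardly moves when termination is similar in the arms. In the case with widely different termination the planned rule loses power, and the bias in the day-30 difference can go either way. The primary analysis is unaffected. Much larger excesses need much higher late-resolution rates, for which the SAP gives no basis. This is a low-priority correction to one secondary endpoint.

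**What to change.** In section 4.7.2:
- Define the endpoint as time to resolution of symptoms without further treatment.
- Keep unresolved subjects who received additional treatment or self-medicated as not resolved to a common end of follow-up (day 30), and do not count a later resolution as an event.
- Censor at last contact only subjects lost or withdrawn for other reasons with unknown status, and define last contact.
- State whether resolution dates after Visit 2 are used, and that these rules, not worst-case imputation, apply to this endpoint.
- Keep the current rule as a labelled sensitivity analysis.

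The cost is SAP wording and minor programming, with no change to conduct or to the primary analysis. Some quartiles may become not reached.
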